The specific aims of this pilot study are: **Aim 1)** *To identify whether no prep ready to eat meals (intervention) or ingredient bundles (control) have higher client acceptability, liking, satisfaction, and perceived diet quality ratings.* **Hypothesis:** No prep ready to eat meals will have higher client acceptability, liking, satisfaction, and perceived diet quality scores than ingredient bundles. **Rationale:** Previous research has shown that acceptance, liking, satisfaction, and perceived diet quality are important determinants of the foods people are willing to eat and the ultimate success of diet-related interventions¹². Aim 1 will establish which strategy is most acceptable and desirable for food pantry clients to inform the development of a future randomized-controlled trial that will aim to test which strategy is most effective at improving objective dietary quality and reducing health-related risk factors. **Aim 2)** *To identify whether no prep ready to eat meals (intervention) or ingredient bundles (control) have higher feasibility ratings with food pantry staff.* **Hypothesis:** No prep ready to eat meals will have higher feasibility ratings than ingredient bundles among pantry staff. **Rationale:** It's unclear how much staff time and pantry resources are needed to put together an ingredient bundle from a recipe or store no prep ready to eat meals in appropriate refrigeration units. This pilot study will determine the resources needed to carry out each program and determine which is preferable and feasible for the pantry staff that would be asked to carry out either model given that staff buy-in is a key component to intervention success¹³.

2. Background.

- Describe past experimental and/or clinical findings leading to the formulation of your study.
- For research involving investigational drugs, describe the previously conducted animal and human studies.
- For research that involves FDA approved drugs or devices, describe the FDA approved uses of this drug/device in relation to your protocol.
- Attach a copy of the approved labeling as a product package insert or from the Physician's Desk Reference.

You may reference sponsor's full protocol or grant application (section number and/or title) or if none, ensure background includes references.

Please respond to all components of this item, or clearly indicate which components are not applicable.

a. Background

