To test the second hypothesis, I will use a mixed-methods approach with food pantry staff (N=10), including questionnaires with fixed and open-ended items on feasibility and satisfaction of each distribution strategy followed by 30-minute semi-structured 1-1 interviews conducted by UT Southwestern study staff.

4. Research Plan / Description of the Research Methods:

4.a. Provide a comprehensive narrative describing the research methods.

- 1) Provide the **order in which tests/procedures will be performed**,
- 2) Provide the **setting** for these events and a description of the **methods used to protect privacy** during the study.
- 3) Provide the **plan for data analysis** (include as applicable the **sample size calculation**)

Please respond to all components of this item, or clearly indicate which components are not applicable.

C.1.5 Intervention Methods

After completing consent forms, participants will be randomized to receive no prep ready-to-eat meals or ingredient bundles using random number generation. Participants will be unaware of their assignment until they are asked to select study meals, in which case it will be obvious because of the food items available to select. Participants will complete questionnaires and then select meals – they can select up to 2-meals, or the bundles needed to make 2-meals, for 14-days for themselves and 2 additional members of their household. Participants will elect to receive one week of meals after selection and come back to pick-up the second week of meals or they will take home all study meals at one time (participants choice). Participants will return at the end of the 2-week study period to complete the follow-up questionnaires and receive payment. A study timeline of intervention components and data collection is provided in **Table 1** to aid visualization of the study plan and timeline for **food pantry clients**.

Table 1. Study plan and timeline for food pantry clients.

Baseline appointment (Day 0)	Intervention (Day 1 - Day 14)	Follow-up appointment (Day 15)

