
 1. Informed consent 2. Randomization 3. Questionnaires (demographics, current pantry use, acceptability, satisfaction, liking, diet quality) 4. Selection of preferred no prep ready-to-eat meals OR ingredient bundles from the available study foods depending on study assignment 5. Follow-up appointment scheduled 	
 1. Participants and family members consume no prep ready-to-eat meals or ingredient bundles at-home for 14-days 2. Depending on the client's preference, reminder phone calls, texts, and/or emails are sent leading up to their follow-up appointment 	
 1. Questionnaires (demographics, current pantry use, acceptability, satisfaction, liking, diet quality) 2. Participant thank you and payment

C.1.5.1 No prep ready-to-eat meals

Roots Food Group provides nutrient-dense dietitian developed no prep ready-to-eat meals to many of the 14 million people on Medi-Cal in California through Aetna and HealthNet. The community-based 501c3 arm of Roots Food Group, Roots Food Foundation, provides the same meals and other resources to people living with blindness at no cost. Roots Food Foundation has agreed to donate and supply meals for this study.

Pantry clients will select study meals for up to 14-days' worth of meals for themselves and 2-members of their household using Crossroads online food selection platform (this platform is already built and is how clients currently select pantry foods). Roots Food Group produces over 70 meals. We have elected to study 14-days of meals to offer clients variety and determine which flavors are most desirable to clients. After ordering, meals will be retrieved from a refrigeration unit, boxed by pantry staff, and brought to the participant to take home. An example dinner is "Teriyaki Chicken with Roasted Potatoes and Broccoli", and an example breakfast is "Omelet with Peppers and Zucchini". Meals can be stored in a refrigerator or freezer and eaten immediately or after reheating depending on the meal and consumer preference. 94% and 86% of Crossroads clients reported owning a refrigerator and microwave respectively when previously surveyed²⁷ and microwaves are available in many community centers and gas stations for public use. This makes no prep ready-to-eat meals a potential solution to many of the challenges faced by Crossroads pantry clients and people experiencing food insecurity.

C.1.5.2 Ingredient bundles

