At the baseline appointment participants will complete informed consent and a questionnaire that includes demographics, typical food pantry utilization, satisfaction, acceptability, liking, and perceived diet quality. Satisfaction items will be adapted from previously validated food pantry client satisfaction surveys (e.g., "How satisfied are you with the amount/variety/frequency of food that you and others in your household receive at this food pantry?")²⁸. Possible responses range from very satisfied and somewhat satisfied to somewhat dissatisfied and very dissatisfied. Liking of study foods will be measured by showing the name and picture of the meal or ingredient bundle and asking participants to respond to a hedonic 9-point bipolar scale with four measures of liking and four measures of dislike and a neutral "neither like nor dislike" item²⁹. Acceptability will be measured by showing the name and picture of the meal and asking the client whether they and/or members of their household ate the meal within the past 2-weeks and whether they would select the meal again if given the opportunity in the future³⁰. Perceived dietary quality will be measured using a single validated item that asks participants to rate their overall diet quality as "excellent," "very good," "good," "fair," or "poor"³¹. At the follow-up appointment, participants will complete the same liking and acceptability ratings, and a similar satisfaction questionnaire and perceived diet quality item, except wording will be slightly modified to "How satisfied were you with the amount of food that you and others in your household received at the food pantry **in the past 2-weeks?**" "How would you rate your dietary quality **over the past 2-weeks?**". These measures will allow us to determine between-group

Form A

IRB # STU 2022-0809

differences at baseline as well as within- and between-group changes in acceptability, satisfaction, liking, and diet-quality after consuming meals over time. These measures will also identify client's preferred meal flavors and frequency as well as the quantity desired in a future intervention.

C.1.6.2. Pantry Staff Measures

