Food pantry staff will answer feasibility items for each of the intervention groups, such as desire to implement each food distribution strategy in the future, perceived appropriateness of the intervention given their organizational goals, perceived sustainability, and financial/staff resources needed to carry out the intervention longer term³². Staff participants will also respond to qualitative open-ended response items such as "Describe any challenges experienced with distributing ingredient bundles" "Describe any challenges experienced with distributing no prep ready-to-eat meals". Responses to the questionnaire will be followed with 30-minute semi-structured 1-1 interviews with study personnel, which give pantry staff the opportunity to directly voice any challenges or preferences that come up when implementing either approach. The pantry personnel perspective will allow us to design a feasible and sustainable longer-term intervention.

C.1.7. Analytic Plan

C.1.7.1. Analytic Plan for Pantry Client Data

Descriptive statistics (e.g., means, percentages, chi-squared tests of independence) will be used to describe participant characteristics and baseline differences. The independent variable of interest will be randomized group assignment (e.g., no prep ready to-eat-meals vs. ingredient bundles). Spearman's correlation and/or repeated measures Analysis of Variance (ANOVA) will be used to describe the association between group assignment and client's perceived diet quality at follow-up. If normally distributed, repeated-measures ANOVA is acceptable and will be used. If non-normal, Spearman's correlation will be used. For the other three outcomes of interest (satisfaction, acceptability, and liking) sum scores will be calculated, and model assumptions will be tested (e.g. residual distributions) before proceeding with repeated-measures Analysis of Variance (ANOVA) to test for group effects on study outcomes of interest and group-by-time interactions.

C.1.7.2 Analytic Plan for Pantry Staff Data

Descriptive statistics (e.g., means, percentages) will be used to describe quantitative items on staff feasibility and satisfaction. Qualitative thematic analysis of open-ended questionnaires and interviews will be synthesized into key findings and suggestions for future intervention development.

Form A

IRB # **STU 2022-0809**

4.b. List of the study intervention(s) being tested or evaluated under this protocol

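### For acceptability, liking and satisfaction, the repeated-measures group effect averages in a Day 0 score taken before supply and so estimates half the Day 15 arm difference; the plan does not say which test decides Aim 1

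*Combined protocol and SAP*

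**What the plan says.** Aim 1 is a comparison between arms: "No prep ready to eat meals will have higher client acceptability, liking, satisfaction, and perceived diet quality scores than ingredient bundles".

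C.1.5 (Intervention Methods) fixes the order on Day 0: "Participants will complete questionnaires and then select meals". Table 1 agrees. Consent, randomization and questionnaires come first, and only then "Selection of preferred no prep ready-to-eat meals OR ingredient bundles from the available study foods depending on study assignment". C.1.5 adds that clients do not know their assignment until they select meals.

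C.1.6.1 (Pantry Client Measures) puts acceptability, liking and satisfaction in the Day 0 questionnaire. Acceptability shows a name and picture and asks "whether they and/or members of their household ate the meal within the past 2-weeks and whether they would select the meal again". On Day 15, "participants will complete the same liking and acceptability ratings"; satisfaction is repeated with slightly changed wording. The section says that the measures will determine between-group "differences at baseline as well as within- and between-group changes in acceptability, satisfaction, liking, and diet-quality after consuming meals over time".

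C.1.7.1 (Analytic Plan for Pantry Client Data) states: "For the other three outcomes of interest (satisfaction, acceptability, and liking) sum scores will be calculated". Repeated-measures ANOVA is then used "to test for group effects on study outcomes of interest and group-by-time interactions". The plan does not say which items enter the acceptability sum, which of the two tests decides Aim 1, or whether a Day 15-only or baseline-adjusted comparison will be made for these three outcomes.

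**The concern.** Two issues arise, of unequal weight.

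The first concerns the hypothesis test. The intervention can act only after Day 0. A group effect in a two-visit repeated-measures ANOVA compares the arms on the average of both visits, so it mixes the visit that carries the effect with one that cannot. The estimate shrinks and, when Day 0 scores vary, power usually falls. This matters because the pilot is meant to tell the later trial which strategy clients prefer.

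The second is specific to acceptability and conditional. On Day 0, the question about having eaten the meal cannot refer to a supplied study meal. If that item is part of the sum, handing out meals raises the score even when clients are no more willing to choose them. A reported within-group gain in acceptability could then largely record supply.

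**Working it through.** **Inputs.** From the documents: 35 per arm (section 3, Study Design), two visits, and questionnaires before meal selection. The documents as supplied give no alpha, SD, correlation, effect size or power target, so there is no planned figure to reproduce. Assumed: two-sided 5%; no expected arm difference on Day 0; a Day 15 difference d = 0.679 in Day 15 SDs, which gives a Day 15-only t-test 80% power. Let k be the Day 0 SD divided by the Day 15 SD, and r the Day 0/Day 15 correlation.

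**Estimates.** These need no SD.
- Group effect: (0 + d)/2 = d/2.
- Group-by-time: d − 0 = d.

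**Standardised effects.** Each is multiplied by √(35/2) = 4.183 for the noncentrality.
- Day 15 only: d
- Group effect: d/√(1 + k² + 2rk)
- Group-by-time: d/√(1 + k² − 2rk)
- Day 15 ANCOVA: d/√((1 − r²)(1 + 1/66)), 67 df

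Worked case, k = 1 and r = 0.2: group effect 0.679/√2.4 = 0.438; group-by-time 0.679/√1.6 = 0.537; ANCOVA 0.679/√(0.96 × 1.015) = 0.688.

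**Power at r = 0 / 0.2 / 0.4** (Day 15 only: 80% throughout)

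| k | Group effect | Group-by-time | Day 15 ANCOVA |
|---|---|---|---|
| 0.1 (near floor) | 80 / 78 / 76% | 80 / 81 / 83% | 79 / 81 / 86% |
| 0.5 | 71 / 64 / 59% | 71 / 78 / 86% | 79 / 81 / 86% |
| 1 | 51 / 44 / 39% | 51 / 60 / 72% | 79 / 81 / 86% |

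**When power is lost relative to Day 15 only.** The group effect loses power when k² + 2rk > 0, that is, when r > −k/2, which covers any zero or positive correlation if Day 0 scores vary. Group-by-time loses power when k² − 2rk > 0, that is, when r < k/2: below 0.5 for k = 1 and below 0.25 for k = 0.5.

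**Supply and the within-group change.** This applies only if both items are coded 0/1 and added over meals. Assumptions: 14 meals, 35 clients in the arm, willingness to select unchanged at 50%, beta-binomial variation between clients (precision 6), paired t-test, 6,000 simulated trials. Chance of a significant within-arm rise:

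| Rise in proportion eaten | Client's willingness the same on both days | Willingness redrawn each day |
|---|---|---|
| 5% to 30% | 99.9% | 96% |
| 5% to 20% | 89% | 63% |
| 10% to 20% | 52% | 31% |

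Scoring willingness alone gives about 5%. With equal arms, the group-by-time false-positive rate is about 5% in every case.

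**The case against.** The strongest reply is that C.1.7.1 also tests group-by-time. With no Day 0 difference, that test estimates the full Day 15 difference and can match ANCOVA (both 86% at k = 0.5, r = 0.4). This stands. A reader might infer that the planned ANOVA as a whole halves the effect or will miss a real one; the documents do not support that. What remains is that the plan names two tests with different estimands and does not say which one answers Aim 1.

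Second, Day 0 acceptability could sit near a floor, for example if willingness to select again is scored only for meals already eaten. The power loss then almost vanishes, although the estimate is still halved. The documents do not settle which case applies.

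Third, the within-group figures concern a test that C.1.7.1 does not list. The intention to examine within-group change comes from one general sentence in C.1.6.1 covering all four outcomes. A reader might also infer that supply biases the arm comparison. It does not follow: both arms are supplied, and the simulated group-by-time error rate stays near 5%.

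Fourth, a Day 0 covariate is not automatically safe. The questionnaire follows randomization, and the liking item shows either the meal or the bundle. If the pictures differ by arm, Day 0 scores could too. The exact halving would then not hold, and adjustment could remove part of the effect. This stands and limits the fix.

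**Conclusion.** The point holds in this limited form. If the arms do not differ on Day 0, as expected when clients do not yet know their assignment, the group effect for acceptability, liking and satisfaction estimates half the Day 15 difference. That part is algebra. The power cost rests on the assumed effect, SD ratio and correlation: 39-71% for the group effect against 79-86% for Day 15 ANCOVA when k is 0.5 to 1 and r is 0 to 0.4, and little loss near a floor. Group-by-time is not halved and ranges from 51% to 86% over the same settings.

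The supply problem is confined to a within-group reading of acceptability, and arises only if eating the meal is part of a sum that the plan leaves undefined. It should be fixed because the plan leaves the deciding test open and a better one is available from data already being collected.

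**What to change.** - In C.1.7.1, for acceptability, liking and satisfaction, make the Aim 1 test the between-arm difference at Day 15, reported with a 95% CI, by ANCOVA on the Day 0 score.
- Define the acceptability score. Score willingness to select separately from having eaten the meal, in the same way in both arms. Report eating as uptake, and do not interpret its within-group change as acceptability.
- Use Day 0 willingness and liking as covariates only if both arms see the same name and picture on Day 0. Otherwise compare Day 15 scores without adjustment. On Day 0, word the willingness item without 'again'.

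Cost: protocol wording and a small questionnaire edit, with no extra visits or participants. The before-after acceptability figure is lost. Compared with an unadjusted Day 15 test, ANCOVA loses about 1 point of power if the correlation is zero (80% to 79%) and gains about 6 at r = 0.4 (80% to 86%).

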have cutting knives or a blender²⁶, these are kitchen tools frequently recommended for healthier meal preparation strategies and required to prepare many recipes, such as stir fries, smoothies, and casseroles.

No prep ready-to-eat meals alleviate the time and food preparation constraints faced by people experiencing food insecurity and provide the opportunity to encourage more nutritious food consumption in a potentially preferable package. While market research and consumer scientists have identified no prep ready-to-eat meals as a burgeoning food retail avenue²⁶, these meals have not been empirically tested as a strategy for improving food security, dietary quality, and health outcomes among clients in a food pantry setting. Given the novelty of this idea, formative research is needed to confirm the intervention is desirable to food pantry clients and feasible for food pantry personnel to carry out.

b. Current practice

[figure not shown]
Currently, food pantry clients at Crossroads receive food in one of three ways:

- 1) Emergency box filled with food provisions filled by pantry staff – the number of pounds received is dependent on the household size and age of household members, the pantry client does not get to choose the food they receive
- 2) With an appointment, clients walkthrough the pantry and select food off shelves and from inside refrigeration units based on a point system – points are distributed based on household size and age of household members and the pantry inventory, the pantry client chooses the food they receive
- 3) With an appointment, clients select food using a web-based application that displays live inventory. Clients select food using the application based on the same in-house point system, the pantry client chooses the food they receive

3. Study Design.

Describe the study design (e.g., single/double blind, parallel, crossover, etc.) Consider inserting a scheme to visually present the study design.

Figure 3. Proposed study design

To test the first hypothesis, I will use a randomized repeated measures between-subjects design with half of the participants randomized to receive 14-days of no prep ready-to-eat meals (intervention, n=35) and half of the participants randomized to receive 14-days of ingredient bundles (control, n=35) (Figure 3).

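### The acceptability item pools the client's eating with the household's, so in a multi-person household a yes does not show whether the client who rates the meal ate it

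*Combined protocol and SAP*

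**What the plan says.** The Aim 1 hypothesis is about acceptability to the client. Section C.1.6.1 (Pantry Client Measures) measures acceptability with two questions per pictured meal. The first is "whether they and/or members of their household ate the meal within the past 2-weeks". The second is "whether they would select the meal again if given the opportunity in the future". Liking is a 9-point rating given by the client for each pictured meal or bundle.

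Both sets of ratings are repeated after the intervention: "At the follow-up appointment, participants will complete the same liking and acceptability ratings".

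Food is provided for more people than the one who answers. Under C.1.5, "they can select up to 2-meals, or the bundles needed to make 2-meals, for 14-days for themselves and 2 additional members of their household". Table 1 expects shared use: "Participants and family members consume no prep ready-to-eat meals or ingredient bundles at-home for 14-days". Section 4.d leaves it to the client how often to eat the meals.

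Section C.1.7.1 turns the answers into scores and compares the arms by repeated-measures ANOVA: "For the other three outcomes of interest (satisfaction, acceptability, and liking) sum scores will be calculated".

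**The concern.** Only the client gives the liking and reselection ratings, but the only described record of exposure to each meal is a household one. Two things follow.

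- **Interpretation of liking.** C.1.6.1 intends the ratings to show change after the meals have been eaten and to identify preferred flavours. Both uses require that the rater has tasted the meal. When only a relative ate it, the Day 15 rating may still be a reaction to a name and a picture.
- **Interpretation of acceptability.** An any-member item rises with the number of potential eaters and with how independently they eat, even when the client's own uptake is unchanged. This quantity is summed into a score that tests a client-level hypothesis. Randomisation balances household size in expectation. It does not balance sharing pattern, which may itself result from the food format assigned.

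Individual exposure cannot be recovered from a pooled answer once the data are in.

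**Working it through.** The plan gives no figure for this item, so there is nothing to reproduce. The check has four steps.

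**Inputs.** From the documents: up to three eaters (client plus two, C.1.5) and 35 clients per arm (section 3). Assumed: individual uptake *p* per meal, the same for every member; the sharing pattern; two-sided alpha 0.05.

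**Step 1. What each answer reveals about the client.**

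| Answer | Household | Client ate the meal? |
|---|---|---|
| No | any | No |
| Yes | client lives alone | Yes |
| Yes | two or more people | Unknown |

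The ambiguity is confined to the last row.

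**Step 2. Effect of sharing pattern on the item.** With *m* eaters:

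- independent eating: P(yes) = 1 − (1 − *p*)^*m*
- all eat or none eat: P(yes) = *p*

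At *p* = 0.5 and *m* = 3, the first is 1 − 0.5³ = 0.875 and the second is 0.50. The gap is 37.5 points.

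Under independent eating, the share of yes answers for meals the client did not eat is (P(yes) − *p*) / P(yes). At *p* = 0.5 this is 0.375 / 0.875 = 42.9%. Under all-or-none eating it is 0.

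| *m* | *p* | Independent | All-or-none | Gap (points) | Yes answers where the client did not eat (independent) |
|---|---|---|---|---|---|
| 3 | 0.3 | 65.7% | 30% | 35.7 | 35.7/65.7 = 54.3% |
| 3 | 0.5 | 87.5% | 50% | 37.5 | 37.5/87.5 = 42.9% |
| 3 | 0.7 | 97.3% | 70% | 27.3 | 27.3/97.3 = 28.1% |
| 3 | 0.9 | 99.9% | 90% | 9.9 | 9.9/99.9 = 9.9% |
| 2 | 0.5 | 75% | 50% | 25.0 | 25/75 = 33.3% |
| 1 | any | *p* | *p* | 0 | 0 |

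**Step 3. Less extreme contrasts.** Let a fraction *r* of meals be all-or-none and the rest independent. With *m* = 3, P(yes) = *rp* + (1 − *r*)[1 − (1 − *p*)³]. If *r* differs by 0.5 between arms, the gap is half the full gap: 0.5 × 35.7 = 17.9, 0.5 × 37.5 = 18.8 and 0.5 × 27.3 = 13.7 points at *p* = 0.3, 0.5 and 0.7. If *r* is the same in both arms, the gap is 0.

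**Step 4. Could 35 per arm detect a gap of this size?** For one meal's yes/no answer, with three eaters and the full contrast, the two-proportion test is significant with probability 0.865, 0.940, 0.888 and 0.472 at *p* = 0.3, 0.5, 0.7 and 0.9. With *r* differing by 0.5, and *p* from 0.3 to 0.7, it is about 0.27 to 0.49. A simulated sum of the two acceptability items used 5 or 14 meals, a t-test at one time point, and an assumed between-client SD of 1 on the logit scale. At full contrast it was significant in 71% to 82% of runs, although individual uptake and willingness to reselect were equal. These are upper-range cases. The arm labels can be swapped in all of them.

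**The case against.** **Direction.** A reader might infer that the item favours the ready-to-eat meals, on the view that these are single portions while a bundle becomes one shared dish. The documents do not support this. C.1.5 and C.1.5.2 describe selection for the client and two household members in the same terms for both arms, and neither portion size nor a shared dish is stated. The opposite is as easy to construct. If individual meals are divided among members, a given pictured meal may reach one person (50% yes at *p* = 0.5), while a cooked dish is offered to three who each accept or refuse it (87.5%). The gap is then 37.5 points in favour of bundles. This objection stands in full.

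**Attenuation.** A reader might also infer that the item always shrinks a true difference. It does not. With three independent eaters in both arms, a 20-point individual difference becomes 97.3 − 87.5 = 9.8 points for 50% v 70%, 87.5 − 65.7 = 21.8 for 30% v 50%, and 65.7 − 27.1 = 38.6 for 10% v 30%. The effect depends on an uptake level that the documents do not give.

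**Total loss of exposure data.** It would be too strong to say that tasted and untasted meals can never be told apart. A no, or a yes from someone living alone, identifies the client's exposure.

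**Household use as the target.** Food is supplied for the household and the satisfaction items also refer to it, so household uptake is a reasonable thing to measure. That stands, and the fix keeps it. It does not justify using the household answer alone in a score for a client-level hypothesis.

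**The form itself.** The questionnaire is not in the documents, and and/or might summarise separate response options. If so, the protocol need only say so. The reselection item is client-level and is not affected.

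**Conclusion.** The point holds in a limited form. That a yes in a multi-person household leaves the client's own exposure unknown follows from the wording alone, as described, and needs no assumption about portions or sharing. How many Day 15 liking ratings are affected is unknown. With three independent eaters it would be 9.9% to 54.3% of yes meals for uptake from 90% down to 30%, and none if the household always eats together.

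The effect on the arm comparison is conditional. It requires sharing to differ between arms. It could then reach 37.5 points on this one item at 50% uptake and three eaters, about 14 to 19 points under the partial contrast at 30% to 70% uptake, and zero if the patterns match. Its sign cannot be read from the documents. These figures show what the wording allows and are not estimates of bias in this trial. This is a cheap improvement to a pilot measure, best made before data collection.

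**What to change.** In C.1.6.1, replace the pooled question with two tick boxes per meal: *I ate it* and *Someone else in my household ate it*. In C.1.7.1, state that the client's answer enters the client acceptability score and that household use is reported separately by arm. At equal individual uptake the client-only item gives P(yes) = *p* in both arms, so the wording artefact is zero at every uptake level.

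At Day 15, report liking for meals the client ate as a supplementary summary beside the score over all pictured meals. Note that it conditions on something that happens after randomisation, so it should not replace the all-meals comparison.

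The cost is one extra tick box per meal, a sentence or two in C.1.7.1, and fewer meals in the tasted-only summary. If the form already records the two answers separately, one clarifying sentence in C.1.6.1 replaces the form change; the scoring and reporting text in C.1.7.1 is still needed.

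### Satisfaction and diet quality gain a two-week recall window at follow-up that they lack at baseline, so within-arm change in these two outcomes cannot be separated from the change in wording

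*Combined protocol and SAP*

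**What the plan says.** Section C.1.6.1 (Pantry Client Measures) describes the two questions as follows.

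- **Satisfaction, Day 0.** The example item is in the present tense and has no time window: "How satisfied are you with the amount/variety/frequency of food that you and others in your household receive at this food pantry". There are four response categories.
- **Satisfaction, Day 15.** The item moves to the past tense and refers to food "received at the food pantry in the past 2-weeks".
- **Diet quality, Day 0.** A "single validated item that asks participants to rate their overall diet quality" on five categories, again with no window.
- **Diet quality, Day 15.** "How would you rate your dietary quality over the past 2-weeks".

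The section states that at follow-up, for these two measures, "wording will be slightly modified". Liking and acceptability are kept the same at both visits. It then says the measures will establish baseline differences between groups "as well as within- and between-group changes in acceptability, satisfaction, liking, and diet-quality after consuming meals over time".

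Section C.1.7.1 (Analytic Plan for Pantry Client Data) makes randomized group the independent variable of interest. For satisfaction, acceptability and liking it plans repeated-measures ANOVA on sum scores "to test for group effects on study outcomes of interest and group-by-time interactions". For diet quality it describes the association between group and the follow-up rating, by repeated-measures ANOVA if the data are normal and by Spearman's correlation if not. It lists no within-arm test.

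**The concern.** A before-after difference within an arm means something only if the same question is asked both times. A client may rate the pantry in general, or the diet overall, differently from the last two weeks even when nothing has changed. Here the change of question falls exactly at the change of visit, for everyone.

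What is at stake is one stated use of the data: the within-group change in satisfaction and diet quality promised in section C.1.6.1, together with any time main effect read from the ANOVA output. An apparent improvement in either arm, or the absence of one, could come partly or wholly from the rewording. The protocol offers no caveat and no means of telling the two apart.

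**Working it through.** The plan states no figure on this point, so there is none to reproduce. The check has two parts.

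**1. What can be estimated**

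Write a_g for the true baseline mean in arm g under the Day 0 wording, d_g for the true change, and w for the shift in ratings caused by the Day 15 wording, taken as the same in both arms.

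- Mean at Day 0: a_g
- Mean at Day 15: a_g + d_g + w

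It follows that:

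| Quantity | Value | Contains w? |
|---|---|---|
| Change within arm g | d_g + w | Yes |
| Time main effect (equal arms) | (d_1 + d_0)/2 + w | Yes |
| Difference between arms at Day 15 | (a_1 − a_0) + (d_1 − d_0) | No |
| Group main effect over both visits | (a_1 − a_0) + (d_1 − d_0)/2 | No |
| Group-by-time interaction | d_1 − d_0 | No |

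As a check, take the four cell means (two arms by two visits) and a design matrix with columns for intercept, group, time, wording and group-by-time. It has 5 columns and rank 4, because the time and wording columns are identical. No analysis of the planned data can separate d_g from w. An arm without study food could have shown the combined effect of time and wording alone, but both arms receive food (section 3, Study Design).

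**2. How much a shift could matter (illustration only)**

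Input from the documents: n = 35 per arm (section 3). Assumed, because the documents give none of these: two-sided 5% level, no true change, correlation r between visits of 0.3 to 0.7, and a shift w in units of the outcome SD, with equal SD at both visits.

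For a paired t-test within one arm:

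- SD of the change = √(2(1 − r)), which is 1.183, 1.000 and 0.775 for r = 0.3, 0.5 and 0.7.
- Noncentrality = w × √35 / SD of the change. For w = 0.2 and r = 0.5 this is 0.2 × 5.916 / 1.000 = 1.183.
- Rejection probability from the noncentral t distribution with 34 degrees of freedom.

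| Wording shift (SD) | r = 0.3 | r = 0.5 | r = 0.7 |
|---|---|---|---|
| 0.1 | 7.7% | 8.9% | 11.5% |
| 0.2 | 16.3% | 21.0% | 31.8% |
| 0.3 | 30.8% | 40.7% | 60.5% |
| 0.5 | 68.0% | 82.0% | 96.0% |

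With no shift the rate is 5%.

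A simulation of 20,000 trials, with a 0.3 SD shift in both arms and r = 0.5, rejected in 41.0% for the within-arm test and 4.9% for the group-by-time test. This agrees with the algebra: the within-arm test is inflated and the interaction test keeps its nominal level.

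**The case against.** The strongest reply is that the planned analysis does not depend on within-arm change. Aim 1 and its hypothesis compare the two strategies. Section C.1.7.1 names group effects and group-by-time interactions, and for diet quality a comparison at follow-up, where everyone answers the same question. The rewording is disclosed and has a sensible motive: a usual-state rating at the start, and a rating of the intervention period at the end. This stands, and it limits the point to the within-group claim in C.1.6.1 and to any time effect that is reported.

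A reader might infer more than the documents support:

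- **That the randomized comparison is biased.** It is not, for a shift shared by both arms. It would be affected only if the rewording acted differently by arm, or through ceiling effects on the four- and five-category scales. Nothing in the documents shows either.
- **That the percentages above are error rates of the planned analysis.** They describe a paired test that the plan does not list, under an assumed shift whose size and direction are unknown.
- **That a false within-arm gain would be carried into the next trial.** The aims section says Aim 1 will show which strategy is preferred, which is a choice between arms, and that the future trial will study objective dietary quality. No documented decision rests on within-arm change.
- **That the mismatch costs precision through a lower correlation between visits.** The documents give no figure from which to show this.

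The full questionnaires are not reproduced: the baseline satisfaction item is an example and the diet-quality item is paraphrased. The protocol nevertheless says itself that both are modified, so the mismatch does not rest on inference.

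Finally, matched wording would not make within-arm change attributable to the meals, since no arm goes without extra food. It removes one source of ambiguity and leaves others, such as regression to the mean.

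**Conclusion.** The point holds for two outcomes and one use. Within-arm change in satisfaction and in perceived diet quality, and any time main effect in either, cannot be separated from the change in wording. This follows from the design alone and needs no numerical assumption.

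Its practical size is unknown. Under the stated assumptions, a shift of 0.2 SD would produce a false within-arm finding in about 16–32% of trials and a shift of 0.3 SD in about 31–61%; at 0.1 SD the figure is about 8–12%.

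Aim 1's between-arm comparison stands, given a shift common to both arms. Liking and acceptability are outside the point because their questions do not change. The correction is worth making because it is cheap before enrolment and, for data already collected under the general wording, cannot be made afterwards.

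**What to change.** **Diet quality.** Ask the item with the same two-week wording at Day 0 and Day 15. The baseline item then departs from its validated wording, as the follow-up item already does.

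**Satisfaction.** Choose one of two options and state it in C.1.6.1:

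1. Use matched two-week wording at both visits. Clients with no recent pantry visit may be unable to answer at Day 0, and some baseline scores would then be missing. A repeated-measures ANOVA on complete cases would lose those clients from the 70. The documents give no visit frequency, so the loss cannot be estimated, and the plan should say how such clients will be handled.
2. Keep the general baseline wording, remove satisfaction from the within-group change claim, and report only the between-arm comparison. This costs nothing in data collection and gives up a result the design cannot deliver.

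The work is an edit to the baseline questionnaire, or to one sentence of the protocol, with no added visits or participants.
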